### **Partial Response**

For PR determination, all the following criteria must be met:

1. 1. A  $\geq 50\%$  decrease in the sum of the product of the diameters (SPD) of up to 6 of the largest dominant nodes or nodal masses.
2. No increase should be observed in the size of other nodes, liver, or spleen, meeting the criteria for progressive disease.
3. Splenic and hepatic nodules must regress by  $\geq 50\%$  in the SPD or, for single nodules, in the GTD.
4. With the exception of splenic and hepatic nodules, other organs should not have any measurable disease.
5. Bone marrow assessment is not required for PR determination.
6. No new sites of disease should be observed.
7. At least 1 PET-positive site of disease (required for the CT+PET assessment of PR).

### **Stable Disease**

1. A subject is considered to have stable disease when he or she fails to attain the criteria needed for a CR or PR, but does not fulfill those for progressive disease.
2. The PET should be positive at 1 or more previously involved sites of disease, with no new areas of lymphoma involvement on the posttreatment CT or PET (for the combined CT+PET assessment of stable disease).

### **Progressive Disease or Relapsed Disease**

Progressive disease or relapsed disease (after CR) is defined as:

1. Lymph nodes should be considered abnormal if the long axis is  $\geq 1.6$  cm, regardless of the short axis length. If a lymph node has a long axis from 1.1 cm to 1.5 cm, it should be considered abnormal, only if its short axis is  $>1.0$  cm. Lymph nodes  $\leq 1.0$  cm x  $\leq 1.0$  cm will not be considered abnormal for progressive disease/relapsed disease.

2. Appearance of any new nodal lesion  $\geq$  1.6 cm in GTD or  $\geq$  1.1 cm in short axis during or after the end of therapy even if other lesions are decreasing in size.
3. Appearance of any new unequivocal extra-nodal lesion measuring  $>$  1.0 cm in GTD, not thought to be benign by the reviewer, even if other lesions are decreasing in size.
4. At least a 50% increase from the nadir in the SPD of any previously involved nodes, or in a single involved node, or in the size of other lesions (e.g. splenic or hepatic nodules). To be considered progressive disease, a lymph node with a diameter of the short axis of less than 1 cm must increase by  $>$  50% and to a size of 1.5 x 1.5 cm or more than 1.5 cm in the long axis.
5. At least a 50% increase from the nadir in the longest diameter of any single previously identified node more than 1 cm in its short axis. For the combined CT+PET assessment of progressive disease, lesions should be PET-positive or the lesion was PET-positive before therapy unless the lesion was too small to be detected with current PET systems (smaller or equal to 1.5 cm in the long axis by CT). Any previously involved FDG positive site that became negative and subsequently became positive will be considered progressive disease. Increased FDG uptake in a previously unaffected site should only be considered progressive disease after confirmation with other modalities. For fluid collection (ascites, pleural, or pericardial effusions) cytology confirmation for presence of lymphoma is required.

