- Treatment will continue until progressive disease or unacceptable toxicity occurs. If progressive disease is diagnosed the subject will discontinue study drug, complete the End of Treatment Visit within 30 days, and enter the Post treatment Phase.
- To assess ibrutinib's influence on T cell behavior and antitumor effect, serial serum samples pre and post therapy will be assessed for Th1 ( (IFN- $\gamma$ ) and Th2 cytokines (IL-10, IL-4 and IL-13) at 4 distinct time points (pre-dose cycle 1 day one, cycle 1 day 2 , cycle 1 day 15) , and cycle 2 day 1 (**See Appendix 1**). All assessments will occur prior to dosing that day. **Patients must be instructed not to swallow study drug prior to biomarker evaluation on cycle 1 day 1, cycle 1 day 2, cycle 1 day 15, and cycle 2 day 1.**
- An End of Treatment Visit will be scheduled within 30 days after the last dose of study drug for all subjects, including those discontinuing treatment for any reason, except for those lost to follow-up, death, or withdrawal of consent for study participation. Subjects who discontinued from treatment (due to progression, adverse event, or other reasons) and enter the Posttreatment Phase should have the End of Treatment Visit completed before starting any subsequent anti-HL treatment. If a subject is unable to return to the site for the End of Treatment Visit, the subject should be contacted to collect adverse events that occur within 30 days after the last dose of study drug.

- **Follow Up Phase**
  - The Posttreatment Phase is the time between the End of Treatment Visit and end of study participation or the end of study. The clinical cutoff for primary analysis will occur approximately 1 year after the last subject is enrolled. Investigators will be informed of the timing of the clinical cutoff. It is imperative that the regularly scheduled disease assessments (clinical and radiographic) are performed throughout the Posttreatment Phase for subjects who discontinue treatment prior to disease progression, as outlined in Section 7.3.1 Evidence of clinical relapse according to the Revised Response Criteria for Malignant Lymphoma is to be documented at the time at which it is first detected. During this period, assessments will be performed until

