##### **Complete Response**

For CR determination, all the following criteria must be met:

1. Complete disappearance of all detectable evidence of disease and disease-related symptoms.
2. All lymph nodes and nodal masses must have regressed on CT to normal size (equal to or smaller than 1.5 cm in the greatest transverse diameter [GTD] for nodes greater than 1.5 cm before therapy, regardless of the short axis). Previously involved nodes that were between 1.1 cm and 1.5 cm in the long axis and more than 1.1 cm in the short axis before treatment must have decreased to or be equal to 1 cm in the short

axis after treatment. All splenic and hepatic nodules and other extranodal disease must have disappeared.

3. PET scan must be negative (for the combined CT+PET assessment of CR). A posttreatment residual mass of any size is permitted as long as it is PET-negative.
4. The spleen and/or liver, if enlarged before therapy on the basis of physical examination or CT scan, should not be palpable on physical examination and should be considered normal size by imaging studies.
5. If bone marrow was involved before treatment, the infiltrate must have cleared on repeated bone marrow biopsy. If a sample is intermediate by morphology, it should be negative by IHC (if bone marrow was involved before therapy and a radiological CR was achieved, but with no bone marrow assessment after treatment, the response should be classified as a PR.)
6. No new sites of disease are detected during assessment.

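### Section 7.3.5 and Appendix 4 set conflicting nodal progression rules with no stated precedence, so a node still within the CR size limit can be PD under one and not under the other

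*Combined protocol and SAP*

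**What the plan says.** **Complete Response (7.3.5).** Item 2 sets the normal-size limit, with a diameter of exactly 1.5 cm also accepted: "smaller than 1.5 cm in the greatest transverse diameter [GTD] for nodes greater than 1.5 cm before therapy, regardless of the short axis". There is no short-axis limit for these nodes. Item 3 adds that "A posttreatment residual mass of any size is permitted as long as it is PET-negative".

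**Progressive Disease or Relapsed Disease (7.3.5).** The list opens "Progressive disease or relapsed disease (after CR) is defined as" and does not say whether any or all items must hold. The CR and PR lists both say all.
- Item 1: "If a lymph node has a long axis from 1.1 cm to 1.5 cm, it should be considered abnormal", provided its short axis exceeds 1.0 cm. A long axis of 1.6 cm or more is abnormal whatever the short axis.
- Item 4: "At least a 50% increase from the nadir in the SPD of any previously involved nodes, or in a single involved node". A final-size floor (1.5 x 1.5 cm, or long axis above 1.5 cm) applies only to nodes with a short axis under 1 cm.
- Item 5: a 50% increase in longest diameter for a node above 1 cm in short axis. It also holds the PET condition, that "lesions should be PET-positive or the lesion was PET-positive before therapy", with an exemption for lesions of 1.5 cm or less in the long axis.

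**Appendix 4, CT column.** Section 7.3.5 refers to this appendix. An individual node is PD with LDi above 1.5 cm, a product increase of at least 50% from nadir, and an increase of 0.5 cm in either diameter for lesions up to 2 cm.

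**Consequences.** Section 9.3.2 ends DOR at progression and PFS at progression or death. Section 7.1.1 states: "If progressive disease is diagnosed the subject will discontinue study drug".

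**The concern.** Two conflicts overlap. Within 7.3.5, a regressed node with long axis 1.1–1.5 cm and short axis above 1.0 cm is normal under CR item 2 and abnormal under PD item 1. Item 4 can then score it as progression without its leaving the CR size range. Between 7.3.5 and Appendix 4, the same pair of scans can be PD by one text and not by the other, and nothing says which prevails.

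The patients exposed are responders with small residual nodes, whose follow-up determines DOR and much of PFS. Two sites could date progression differently on identical measurements, and the date treatment stops would differ with it.

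**Working it through.** The plan gives no figure to reproduce here, so the check applies the rules to node measurements.

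**1. Growth that item 4 requires.** For equal proportional growth, a 50% rise in the product needs √1.5 − 1 = 22.5% per diameter. That is about 2.2, 2.5, 2.7 and 3.4 mm for diameters of 10, 11, 12 and 15 mm. Item 5 asks for 50% in the longest diameter, which is 6 mm for a 12 mm node.

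**2. Worked nodes** (each above 1.5 cm before therapy, then regressed to the nadir shown):

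| Nadir (cm) | Later scan (cm) | Product ratio | 7.3.5 items 1 and 4 | Within CR size limit | Appendix 4 CT rule |
|---|---|---|---|---|---|
| 1.1 x 1.0 | 1.4 x 1.2 | 1.68/1.10 = 1.53 | PD | yes | not PD |
| 1.1 x 1.1 | 1.4 x 1.3 | 1.82/1.21 = 1.504 | PD | yes | not PD |
| 1.2 x 1.1 | 1.5 x 1.4 | 2.10/1.32 = 1.59 | PD | yes | not PD |
| 1.2 x 1.2 | 1.5 x 1.5 | 2.25/1.44 = 1.56 | PD | yes | not PD |
| 1.2 x 1.1 | 1.5 x 1.1 | 1.65/1.32 = 1.25 | not PD | yes | not PD |

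The first four fail Appendix 4 twice: the long axis does not exceed 1.5 cm, and neither diameter grew by 0.5 cm. None is PD under item 5. The last row shows that 3 mm in one diameter alone is not enough.

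**3. Which nodes are affected.** The largest node within the CR limit is 1.5 x 1.5 = 2.25 cm². With a nadir short axis of at least 1.0 cm, item 4 can be met inside that limit when the nadir product is at most 2.25/1.5 = 1.50 cm².

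**4. Grid check.** All 51 shapes with long axis 10–15 mm and short axis from 5 mm up to the long axis were run in 1 mm steps.
- Short axis 10 mm or more (21 shapes): under 7.3.5, 16 reach PD with at most 3 mm per axis and 5 with 4 mm. Some of these end above 1.5 cm.
- Short axis under 10 mm (30 shapes): 15 reach PD with 2–3 mm, for example 1.4 x 0.6 to 1.6 x 0.8 cm (1.28/0.84 = 1.52). Item 4's floor makes the others need 4–6 mm.
- Appendix 4: every shape needs at least 5 mm in one axis (5 mm in 45 shapes, 6 mm in 6).
- Growth of 2–3 mm in one axis alone never gives PD under 7.3.5.

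**5. PET.** A target node should have been PET avid at selection (7.3.3), so it meets the PET condition through its pre-therapy status. A currently negative PET would not reverse the call under that wording.

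**6. Illustration of reading error.** Assumptions, none from the documents: a truly stable 1.2 x 1.1 cm node, independent Gaussian error in each diameter, readings rounded to 1 mm, comparison with the running nadir, 40,000 simulated patients. Five scans match weeks 8, 20, 32, 44 and 56 of the 7.3.1 schedule.

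| Error SD | Nodes | False PD, 7.3.5 | False PD, full Appendix 4 rule |
|---|---|---|---|
| 1.0–1.5 mm | 1 | 5–13% | 0–2% |
| 1.0–1.5 mm | 3 | 15–34% | 0–5% |

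With three scans, the 7.3.5 figures fall to about 2–6% (one node) and 5–16% (three). At SD 2 mm they rise to 21% and 51%. A rule with only a floor of long axis above 1.5 cm then gives about 12% and 32%. Appendix 4 is stricter than that floor alone, so its rates cannot be higher, but neither rule is then immune.

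**The case against.** The strongest reply is that the protocol has safeguards. PET is required at relapse from CR (7.3.1, 7.3.2), Appendix 1 marks PET/CT under Suspected PD, the investigator judges disease status for continuing treatment (7.2.0), and Section 8.2 speaks of overt progression. These make an automatic stop on a 3 mm change less likely. They do not repair the wording: item 4 is met, the PET condition is met through pre-therapy status, and the progression date for DOR and PFS still has to come from one of two rules.

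It is also fair that the simulated rates are conditional. The documents give no reading error, no number of residual nodes and no number of patients expected to be in CR with such a node. Five stable scans also presuppose regression by the first one.

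A reader might infer more than the text supports:
- *That any node of 1.5 cm or less is caught, or that 2–3 mm in one diameter is enough.* Growth is needed in both diameters, and the normal/abnormal clash is confined to long axis 1.1–1.5 cm with short axis above 1.0 cm.
- *That smaller nodes must always pass 1.5 cm.* Item 4's floor also accepts 1.5 x 1.5 cm, so a 0.9 x 0.9 cm node can be PD there, still within the CR size limit.
- *That item 1 alone makes an unchanged 1.5 x 1.2 cm node PD.* This follows only if the unlabelled list is read as any one of its items. Item 1 reads more naturally as a definition, but the text does not say so.
- *That the primary result is biased.* No effect on ORR is shown. A CR already documented would still count if best response is used, which the documents do not state.

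**Conclusion.** The conflict is real and can be shown from the text alone. A node going from 1.1 x 1.1 to 1.4 x 1.3 cm (+50.4%) or from 1.2 x 1.2 to 1.5 x 1.5 cm (+56%) meets the CR size limit, is PD under 7.3.5, and is not PD under Appendix 4's CT rule. That part needs no assumption beyond reading Appendix 4's nodal conditions as joint requirements.

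Its reach is limited to the secondary endpoints DOR and PFS, which are reported as Kaplan-Meier medians without a test, and to the date treatment stops. The false-PD rates show that the choice of text can matter. They are not a forecast for this trial, because they rest on assumed reading error, stable nodes and a fixed number of scans.

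**What to change.** - Reconcile CR item 2, PD items 1, 4 and 5, and Appendix 4 into one nodal PD rule, or state which text governs, so that one node measurement cannot be both CR-normal and PD. Which size and growth limits to use is for the sponsor to decide.
- Mark PD item 1 as a definition, and state that PD is any one of the remaining items.
- State that DOR and PFS are scored by that single rule at all sites.

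Copying only Appendix 4's long-axis condition into item 4 would not be enough. A node going from 1.3 x 1.0 to 1.6 x 1.3 cm (2.08/1.30 = 1.60, +60%) would then be PD under 7.3.5 after 3 mm per diameter, but still not under Appendix 4, which also asks for a 0.5 cm increase. Item 1 would also still conflict with CR item 2.

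The cost is protocol wording only, with no extra scan or visit. Depending on the rule chosen, true regrowth of a small node may be called PD up to one scan later.

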#### **7.4 Sample Collection and Handling**

Correlative studies evaluating blood samples for T cell behavior and cytokine expression as well as fluorescence in situ hybridization of tumor samples are required during this study. For blood samples, study kits will be provided with shipping instructions. A detailed description of these instructions are noted in the **Lab Manual**.

For tissue block submission, a representative amount of tissues in a paraffin embedded block should be shipped to the address noted in the **Lab Manual**.

**The appropriate personnel at the Karmanos Cancer institute (noted on instructions) should be notified at least 24 hours prior to shipment.**

### **8 SUBJECT COMPLETION AND WITHDRAWAL**

#### **8.1 Completion**

A subject will be considered to have completed the study if he or she has died before the end of the study, has not been lost-to-follow up, or has not withdrawn consent before the end of the study.

#### **8.2 Withdrawal from Study Treatment**

Investigators are encouraged to keep a subject experiencing clinical benefit in the study unless significant toxicity puts the subject at risk or routine noncompliance puts the study outcomes at risk.

If a subject's study treatment must be discontinued this will not result in automatic withdrawal of the subject from the study.

A subject's study treatment should be discontinued if:

- The subject experiences overt disease progression or relapse
- Unacceptable toxicity
- The subject becomes pregnant
- The subject refuses further treatment with the study drug
- A serious protocol violation has occurred, as determined by the principal investigator

The investigator must notify the medical monitor within 24 hours if a subject has been determined to have disease progression and provide documentation of disease progression. If a subject discontinues study treatment before the onset of disease progression, end of treatment and posttreatment assessments should be obtained and follow-up of scheduled assessments should be continued.

Refer to Section 7.1.1 for instructions regarding the posttreatment efficacy assessments. The reason(s) a patient discontinues treatment will be recorded on the CRF.

### **8.3 Withdrawal from Study**

A subject will be withdrawn from the study for any of the following reasons:

- Lost to follow-up
- Withdrawal of consent

If a subject is lost to follow-up, every reasonable effort must be made by the study site personnel to contact the subject and determine the reason for discontinuation/withdrawal. The measures taken to follow up must be documented. When a subject withdraws before completing the study, the reason for withdrawal is to be documented in the CRF and in the source document. Study drug assigned to the withdrawn subject may not be assigned to another subject. A subject who withdraws will not be replaced.

## **9. STATISTICAL CONSIDERATIONS**

### **9.1. Objectives**

The primary objective is estimation of the overall response rate. Secondary objectives are estimation of duration of response and progression free survival. The exploratory objectives are identification of genes of interest, estimation of the T cell subset alteration and estimation of the association of PDL1 and PDL2 overexpression by FISH with overall response.

### **9.2. Design**

This is a multicenter, single arm, single stage phase II study designed to estimate the efficacy of ibrutinib in evaluable patients with relapsed, refractory Hodgkin's lymphoma. A participant will be deemed response evaluable if he/she has completed at least one cycle of therapy, has at least one imaging study (CT, MRI or PET) and has not missed >25% of treatment dose (14 doses) prior to cycle 3 day 1. Any participant receiving at least 1 dose of ibrutinib will be considered evaluable for toxicity analysis.

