	
 
• Requires treatment with a strong cytochrome P450 (CYP) 3A4/5 inhibitor. (see Appendix 3)
 
• Currently active, clinically significant hepatic impairment Child-Pugh class B or C according to the Child Pugh classification
 
• Lactating or pregnant.
 
• Unwilling or unable to participate in all required study evaluations and procedures.
 
• Unable to understand the purpose and risks of the study and to provide a signed and dated informed consent form (ICF) and authorization to use protected health information (in accordance with national and local subject privacy regulations).
 

Study Treatment:	Ibrutinib 560mg p.o. q.d. until disease progression, unacceptable toxicity or patient/clinician choice to discontinue.
Concomitant Therapy:	Refer to Section 6 for information on concomitant therapy.
Safety Plan:	The Barbara Ann Karmanos Cancer Institute, Data and Safety Monitoring Committee (DSMC), provides the primary oversight of data and safety monitoring for KCI Investigator-initiated trials. In Addition monthly investigator teleconferences will occur to discuss adverse event and safety issues.
Statistical Methods and Data Analysis:	
All efficacy analyses will be performed using all evaluable participants.
 
Primary Efficacy Analysis:  A one-sample binomial test will be used to assess efficacy in terms of ORR. The ORR will be reported as a proportion with a one-sided, lower 95% confidence interval. Assuming p0=30%, pA=50%, power=85% and type I error = 10.69% the null hypothesis will be rejected if there are 13 or more ORRs.
 
Secondary Efficacy Analysis:  DOR will be reported as median and range. Kaplan-Meier estimate of median PFS will be reported with 95% confidence intervals.
 
Exploratory Efficacy Analysis:

	
The influence of ibrutinib on T cell behavior and antitumor effect will be assessed using a variety of techniques including gene expression and mutational analysis. T cell subset alterations in blood and tumor tissue will be analyzed and PD-1 and PD-2 expression will be evaluated by FISH and IHC.
 
Safety Analysis:
 
Frequency of grade 3 or higher adverse events will be tabulated and all grade 1 and 2 adverse events will be collected.

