The Treatment Phase will extend from the administration of the first dose of ibrutinib until the completion of the End of Treatment Visit. Subjects will receive 560 mg oral ibrutinib once daily on a 28-day cycle until disease progression (or relapse if the subject achieved a CR) or occurrence of unacceptable toxicity, whichever occurs first. Regularly scheduled disease assessments are required throughout the Treatment Phase to assess Efficacy (**See appendix 1**). PET imaging is required to document complete remission (CR). PET imaging is to be performed after 2 cycles of therapy, at the time of maximal tumor reduction (e.g., CR or 2 consecutive CT scans showing no further tumor reduction), relapse from CR, and at suspected disease progression if new lesion was detected on CT. Tumor (from lymph node biopsies or diagnostic biopsy tissue collected during screening), blood, and/or bone marrow aspirate/ biopsy will be evaluated to identify markers predictive of response to ibrutinib. Bone marrow biopsy will be used to confirm CR if marrow involvement is present at baseline. During the study, safety evaluations will include adverse event monitoring, physical exams (including changes to concomitant medications and assessment of lymphoma B-symptoms), and clinical laboratory parameters (**See Appendix 1**). Subjects will be provided a diary card to record study drug intake (**See Appendix 6**). At each site visit, site personnel will check ibrutinib daily dosing and evaluate the subject for toxicity; doses can be held or reduced based on the severity of and the recovery from a previous toxicity. Dose re-escalation will ONLY be allowed after discussion with medical monitor, otherwise no dose escalation will be permitted. Subjects who discontinue from treatment will enter the Posttreatment Phase. Regularly scheduled disease assessments are required during the Posttreatment Phase for subjects who discontinue treatment prior to disease

progression, until the clinical cutoff. During the Posttreatment Phase, data on PFS, overall survival, and subsequent anti-HL therapies will be collected from all subjects except those who explicitly withdraw consent for further follow-up. It is imperative that survival status be assessed and that the date of death is documented for each treated subject.

CONFIDENTIAL

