## 5.5. Criteria for Permanent Discontinuation of Study Drug

Study drug may be held for a maximum of 28 consecutive days. Study treatment should be permanently discontinued in the event of a toxicity lasting >28 days. Once the ibrutinib dose is reduced it cannot be re-escalated without a discussion with the medical monitors ([name] or [name]).

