## 7.2.0 Efficacy Evaluations

The investigator will perform tests that will allow evaluation of response to therapy according to the Revised Response Criteria for Malignant Lymphoma. An evaluable patient will be defined as “any patient receiving study drug for > 1 cycle and having completed at least one radiographic (CT with contrast or PET) evaluation. Patients missing > 25% (14 doses) of study drug prior to the initial study evaluation (cycle 3 day 1 +/- 7days) will not be evaluable for efficacy but may remain on study pending a discussion with the medical monitors [name] or [name]. Efficacy assessments will be performed as outlined in **Appendix 1** and **Section 7.3**. These assessments are to be conducted until disease progression, withdrawal of consent from study participation, or the end of study. For subjects who discontinue study drug before disease progression is documented, disease assessments will continue in the Posttreatment Phase. The determination of disease status for continuation of treatment will be assessed by the investigator based on the results of the efficacy assessments. For all subjects, documentation of disease progression must be sent within 24 hours to the sponsor's medical monitor.

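### Efficacy is analysed only in patients whose evaluability depends on events after dosing, with no all-treated analysis beside it, two slightly different definitions and one fixed cut-off

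*Combined protocol and SAP*

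**What the plan says.** The synopsis (Statistical Methods and Data Analysis) states: "All efficacy analyses will be performed using all evaluable participants". The response-rate, duration-of-response and PFS analyses are listed beneath that sentence. Section 9.2 describes the trial as "designed to estimate the efficacy of ibrutinib in evaluable patients".

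Evaluability is defined twice:

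- **Section 7.2.0:** "any patient receiving study drug for > 1 cycle and having completed at least one radiographic (CT with contrast or PET) evaluation". A patient over the missed-dose limit before the initial evaluation (cycle 3 day 1, plus or minus 7 days) "will not be evaluable for efficacy but may remain on study pending a discussion with the medical monitors".
- **Section 9.2:** one completed cycle or more, one CT, MRI or PET, and a patient who "has not missed >25% of treatment dose (14 doses) prior to cycle 3 day 1".

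The only all-treated set is for safety: "Any participant receiving at least 1 dose of ibrutinib will be considered evaluable for toxicity analysis" (section 9.2). Section 3.1 says that "data on PFS, overall survival, and subsequent anti-HL therapies will be collected from all subjects", except those who withdraw consent to follow-up. Sections 9.3.2 and 9.4.1 define and analyse PFS without naming a population. Sections 9.4.1 and 9.5 give a single rejection rule, 13 or more responders, which section 9.5 ties to 31 evaluable patients.

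**The concern.** The analysis set is selected partly by how a patient fares in the first weeks. Under either definition, a treated patient who dies, progresses clinically or stops for toxicity in cycle 1 is outside it. Such a patient has no response, and a death or progression would be a PFS event under section 9.3.2. If excluded patients respond less often than included ones, the evaluable rate overstates the rate among everyone treated.

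That direction is likely but not certain. Section 5.5 states: "Study drug may be held for a maximum of 28 consecutive days". A hold of 15 to 28 days early in treatment also passes the 14-dose limit, so a patient who later responds can be excluded too.

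The stated purpose (Objectives, Primary Objective) is to judge whether activity justifies further study. Without an all-treated result, a reader cannot tell how far that judgement depends on the selection. In an open-label trial, unclear evaluability rules also leave room to settle borderline patients after their outcome is known.

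**Working it through.** **1. The plan's own figures.** Inputs (synopsis and section 9.5): 31 evaluable, null 30%, alternative 50%, one-sided target 11%, reject at 13 or more. Exact binomial:
- P(X ≥ 13 | 31, 0.30) = 0.1069, matching the stated 10.69%.
- P(X ≥ 13 | 31, 0.50) = 0.8595, against the stated 85%.

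The rule is correct for evaluable patients.

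**2. The dose threshold.** Two 28-day cycles are 56 doses, and 0.25 × 56 = 14. The 25% and the 14 agree.

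**3. A boundary result on the two denominators.** Assume 35 treated and 4 excluded.
- Evaluable: 13/31 = 41.9%.
- All treated, none of the 4 responding: 13/35 = 37.1%.
- All treated, 2 of the 4 responding: 15/35 = 42.9%.

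The difference can go either way. The 4 is an assumption, taken from 35 − 31. It is not a limit fixed by the documents: section 9.5 says 35 will be consented, while section 3.1 says about 35 will be enrolled.

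**4. The two definitions side by side.**

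| | Section 7.2.0 | Section 9.2 |
|---|---|---|
| Exposure | more than 1 cycle | 1 cycle or more |
| Imaging | CT with contrast, or PET | CT, MRI or PET |
| Doses counted up to | initial evaluation, cycle 3 day 1 ± 7 days | cycle 3 day 1 |
| Doses after permanent stop | not stated | not stated |

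A patient whose last dose is on day 28 meets the exposure criterion only under section 9.2.

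The last row also matters. Suppose doses after stopping count as missed, and counting runs to cycle 3 day 1 (56 doses). A last dose on day 28 leaves 56 − 28 = 28 missed, and one on day 41 leaves 56 − 41 = 15. Both are excluded, even with progression shown on a scan. A last dose on day 42 leaves 14, which is not over the limit. If section 7.2.0 is applied with a scan on day 50 (49 doses before it), last doses on days 35 to 41 leave 49 − 35 = 14 down to 49 − 41 = 8, so the limit does not exclude them. If doses after stopping do not count as missed, none of these patients is excluded on this ground.

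**5. The cut-off when the evaluable number is not 31.** Keeping 13:
- 28 evaluable: alpha 0.0491, power 0.7142.
- 35 evaluable: alpha 0.2271.

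Smallest count with exact one-sided alpha at most 0.11:

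| Evaluable | Cut-off | Alpha | Power at 50% |
|---|---|---|---|
| 28 | 12 | 0.1028 | 0.8275 |
| 29 | 13 | 0.0652 | 0.7709 |
| 30 | 13 | 0.0845 | 0.8192 |
| 31 | 13 | 0.1069 | 0.8595 |
| 32 | 14 | 0.0694 | 0.8115 |
| 33 | 14 | 0.0884 | 0.8519 |
| 34 | 15 | 0.0571 | 0.8042 |
| 35 | 15 | 0.0731 | 0.8447 |

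**6. PFS.** The documents do not allow a size to be calculated.

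**The case against.** An evaluable primary set is a declared design choice and common in single-arm phase II trials. Section 9.2 names evaluable patients as the target, and section 9.5 attaches the 30% and 50% to the 31. That stands, and it is why the primary analysis should be kept.

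A reader might infer that the true type I error is about 22%. That figure arises if the 30% null refers to all treated patients and 4 excluded patients never respond: the evaluable rate is then 0.30 × 35/31 = 0.3387, and P(X ≥ 13 | 31, 0.3387) = 0.2215. Sections 9.2 and 9.5 do not support this. Their natural reading is a null for evaluable patients, for which alpha is 10.7%.

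A reader might also infer that PFS is firmly restricted to evaluable patients. The restriction rests on the synopsis sentence and the efficacy wording in 7.2.0. Section 9.2 speaks of response evaluability, and sections 9.3.2 and 9.4.1 set no limit for PFS. The documents are unclear here rather than decided.

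Nor can it be said outright that patients who stop between days 28 and 41 are excluded. That needs counting to cycle 3 day 1 and treating doses after discontinuation as missed. Section 5.2 uses the word for a dose that was due and not taken, which favours the other reading. A clarifying clause settles it.

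The conflict between definitions is narrow. The exposure difference touches only patients stopping at exactly one cycle, and section 7.3.1 says MRI does not replace the required CT. A cut-off for another evaluable number can be derived from the 11% target, but the plan does not say that it will be. None of this supplies the missing all-treated analysis.

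**Conclusion.** The point holds as a should-fix. Patients who fail in cycle 1 are outside the response-rate denominator under both definitions, and outside the PFS analysis if the synopsis sentence is taken at its word. No planned analysis shows what that does to the result.

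The sample-size arithmetic and the 13-of-31 rule are sound. The possible shift is illustrated by 41.9% against 37.1% at the boundary, assuming 4 excluded non-responders; the actual number excluded and their response rate are unknown. The definition conflict and the single cut-off are smaller matters, but they bear on the primary denominator and decision rule. Section 8.3 does not replace withdrawals, so exactly 31 evaluable is not assured.

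**What to change.** Keep the evaluable primary analysis and make three changes.

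1. In section 9.4.1 and the synopsis, pre-specify a supportive response-rate and PFS analysis of everyone who receives a dose. Count anyone without a documented CR or PR as a non-responder. Report it beside the evaluable result.
2. Merge sections 7.2.0 and 9.2 into one evaluability definition that says whether doses after permanent discontinuation count as missed.
3. In sections 9.4.1 and 9.5 and the synopsis, state that the cut-off is the smallest count with exact one-sided alpha at most 11% for the actual evaluable number: 12 for 28; 13 for 29 to 31; 14 for 32 and 33; 15 for 34 and 35.

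Counting early deaths, progressions and toxicity stops as non-responders within the primary set would change the primary population. That is open to the sponsor but is not part of this fix.

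The cost is a wording amendment, with the company and IRB review described in sections 12.1 and 12.7, and a small extra analysis on a set already defined for toxicity. No new procedures are needed. The all-treated rate is likely to be slightly lower than the evaluable one. Holding alpha at or below 11% leaves power at 50% under 85% for every evaluable number from 28 to 35 except 31 and 33, with a low of 77% at 29.
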